Following the block, subjects will proceed to the operating room where they will undergo a standard general anesthetic with endotracheal intubation (desflurane or isoflurane in a mixture of air/oxygen). The dosing of intraoperative opioids will be left to the discretion of the attending anesthesiologist in the room.

In the Post-Anesthesia Care Unit (PACU) and on the postoperative floor, subjects will have access to oxycodone 5-15 mg PO q3h prn for rescue analgesia (the primary outcome measure). In the PACU, patients will also have access to intravenous hydromorphone if the oral opioid

provides inadequate relief. Finally, subjects may receive a standard multimodal analgesia regimen consisting of:

- Acetaminophen 975 mg PO q6h (beginning in preop holding)
- Gabapentin 600 mg PO once in holding, then 100 mg PO tid thereafter
- Ketorolac 15 mg IV prior to skin closure

While this standard regimen is expected, it may vary per clinical care team judgement and/or preference. Any alterations in this standard regimen will not be considered a protocol deviation.

Assessments

Patient assessments will be performed or recorded by a research assistant twice daily (unless otherwise specified). Assessments made after discharge will be recorded by subjects who will be provided with a diary to document the outcomes. Outcomes to be measured include:

Opioid consumption. Cumulative opioid consumption over 48 hours is the primary outcome measure. Data will be drawn from PACU records and from the nursing medication records on a twice-daily basis. Post discharge opioid use will be tracked in the take-home patient diary. The patient will be called at 7 days after surgery to collect.

NRS-11. The 11-point Numeric Rating Scale (0-10) will be used as a secondary outcome measure. Two measures will be taken with each assessment, one at rest and one with coughing. These will be conducted preoperatively, 30 minutes after arrival to PACU, and at time points 8 hrs., 24 hrs., 36 hrs. 48 hrs, 72 hrs, 96 hrs., 120 hrs., 144 hrs. and 168 hrs.

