Historical data of 30 patients that meet inclusion criteria and meet no exclusion criteria, will be collected and for the retrospective group. The anesthesia statisticians will evaluate the following data from the patient's electronic medical record if available, including but not limited to hospital notes, anesthesia notes, medical history, medications, pain service notes, and flowsheets from admission to discharge. Electronic medical records will be used to assess the following items to compare to the prospective cohort.

Opioid consumption. Cumulative opioid consumption at 24hours, 48 hours and 72 hours. 48 hours is the primary outcome measure. Data will be drawn from PACU records and from the nursing medication records.

NRS-11. The 11-point Numeric Rating Scale (0-10) will be used as a secondary outcome measure. These will be collected from the preoperative assessment record, 30 minutes after arrival to PACU, and at time points 8 hrs., 24 hrs., 36 hrs. 48 hrs. and 72 hrs.

Thoracic epidural success and adverse events. Evidence of epidural block success/failure (as described in the anesthesia record and in daily Inpatient Pain Service notes). This will be done at the time of pain assessment (30 minutes after arrival to PACU, and at time points 8 hr, 24 hr, 36 hr and, 48 hr and 72 hr). Subject data will be collected for potential adverse events related to the epidural including evidence of hypotension, urinary retention, inability to ambulate per physical therapy. (known possible side-effect of thoracic epidural approach).

Hospital length of stay. Measured both by raw length of stay and by time to achieving "discharge readiness", defined by the presence of 3 criteria: a pain score of 3 or less with ambulation, no opioids required in the preceding 6 hours, and the ability to perform self-care (go to the toilet, dress, and shower).

Incidence of opioid-related adverse events. Incidence of nausea, vomiting, ileus, constipation, orthostasis, pruritis, urinary retention, respiratory depression

Time to first mobilization. Measured from time of arrival in PACU (time zero)

Cost. Hospital costs including pharmacy-related costs, costs due to opioid-related adverse events, the cost associated with nursing interventions and drugs to treat opioid-related adverse events, and overall hospital admission costs will be calculated.

Selection of Subjects

Criteria for inclusion in Prospective cohort:

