We will use descriptive statistics (mean (SD) or frequency (%)) and group comparisons via Wilcoxon rank sum or fisher exact tests to measure differences between cohorts in opioid consumption, pain scores with rest and activity, and other secondary outcome measures.

Sample Size Justification

A difference in opioid consumption less than 20% would be considered non-inferior. Based on typical postoperative opioid consumption following laparoscopic colectomy (20mg +/- 5.2 mg), a total of 54 subjects (27 in each group) would be required to reject the null hypothesis that QL blockade is inferior in the first 48 hours with the study intervention, given an alpha of 0.05 and a power of 0.8. We plan on recruiting 45 subjects to account for dropout.

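### The study is sized to reject inferiority at a 20% margin, but the planned Wilcoxon test of 48-hour opioid use does not use the margin, and no decision rule is given.

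*Combined protocol and SAP*

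**What the plan says.** Under Assessments, "Cumulative opioid consumption over 48 hours is the primary outcome measure".

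Sample Size Justification frames the study as non-inferiority: "A difference in opioid consumption less than 20% would be considered non-inferior". It continues that "a total of 54 subjects (27 in each group) would be required to reject the null hypothesis that QL blockade is inferior", "given an alpha of 0.05 and a power of 0.8". The planning value is "typical postoperative opioid consumption following laparoscopic colectomy (20mg +/- 5.2 mg".

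The analysis text, under Data Analysis & Statistical Considerations, is a single sentence covering all outcomes. Besides descriptive mean (SD) or frequency (%), it plans "group comparisons via Wilcoxon rank sum or fisher exact tests to measure differences between cohorts in opioid consumption". Fisher's test suits categorical outcomes, so the Wilcoxon test is the only inferential method for the primary outcome.

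On group sizes, the retrospective paragraph of Assessments specifies "Historical data of 30 patients that meet inclusion criteria", and Sample Size Justification ends "We plan on recruiting 45 subjects to account for dropout".

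**The concern.** The hypothesis and the analysis do not meet. The sample-size null is that QLB is worse by at least the margin; the ordinary Wilcoxon null is that the cohorts do not differ. Failing to reject the second says nothing definite about the first. No section gives a confidence interval, a margin-shifted test or a rule for declaring non-inferiority.

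The 20% sentence does not fill the gap. It leaves open:

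- whether 20% is compared with a point estimate or a confidence limit;
- whether it is 20% of the observed TEA value or of the 20 mg planning mean (4 mg);
- whether alpha 0.05 is one- or two-sided;
- what the milligrams measure. Design & Procedures attaches the primary-outcome label to oral oxycodone rescue but also allows IV hydromorphone in the PACU. A morphine equivalent appears only in the eligibility criteria.

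Purpose of the Study expects roughly equal opioid use, so a non-significant difference test is a likely result and could easily be reported as success. The rule behind such a claim would then be settled after the data were seen, and the two informal rules the text leaves open do not hold the stated alpha.

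**Working it through.** **Inputs.** From Sample Size Justification: mean 20 mg, 5.2 mg (read as the SD), margin 20%, alpha 0.05, power 0.80, 27 per group. From the retrospective paragraph of Assessments: 30 historical patients. Assumed: normal data, equal SDs, and true difference 0 for power.

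**1. The plan's own figure.** The margin is 0.20 × 20 = 4 mg. The normal formula is n per group = f (z_α + z_β)² × 5.2²/4², where 5.2²/4² = 1.69. For a fixed 4 mg margin, f = 2. For a margin relative to the observed TEA mean, f = 1 + 1.2² = 2.44.

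| Margin | One-sided alpha | Calculation | n per group |
|---|---|---|---|
| Fixed 4 mg | 0.025 | 2 × 7.849 × 1.69 = 26.5 | 27 |
| Fixed 4 mg | 0.05 | 2 × 6.183 × 1.69 = 20.9 | 21 |
| Relative 20% | 0.025 | 2.44 × 7.849 × 1.69 = 32.4 | 33 |
| Relative 20% | 0.05 | 2.44 × 6.183 × 1.69 = 25.5 | 26 |

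The simplest reading, fixed 4 mg at one-sided 0.025, gives exactly 27. A two-sided superiority calculation for 4 mg has the same algebra and also gives 27, so it is the wording of the null that marks the design as non-inferiority.

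**2. Power at the stated and possible sizes** (noncentral t, true difference 0).

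| QLB vs TEA | Margin | One-sided 0.025 | One-sided 0.05 |
|---|---|---|---|
| 27 vs 27 | Fixed 4 mg | 79.2% | 87.4% |
| 27 vs 27 | Relative 20% | 70.9% | 81.1% |
| 15 vs 30 | Fixed 4 mg | 66.2% | – |
| 15 vs 30 | Relative 20% | 60.3% | – |
| 45 vs 30 | Fixed 4 mg | 89.6% | – |
| 45 vs 30 | Relative 20% | 81.7% | – |

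The 15 vs 30 rows read 45 as the total; the 45 vs 30 rows read it as the prospective cohort. The normal formula at 27 vs 27 and one-sided 0.025 gives 80.7% (fixed) and 72.5% (relative). By t, 80% power at one-sided 0.025 needs 28 per group (fixed) or 34 (relative; 33 gives 79.6%).

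**3. How often each rule would wrongly pass QLB.** Simulation, 40,000 studies per setting, TEA mean 20 mg, SD 5.2 mg, QLB truly 4 mg higher.

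| Rule | QLB vs TEA | Wrongly called non-inferior |
|---|---|---|
| Wilcoxon p ≥ 0.05 | 27 vs 27 | 23.4% |
| Wilcoxon p ≥ 0.05 | 15 vs 30 | 36.1% |
| Wilcoxon p ≥ 0.05 | 45 vs 30 | 12.0% |
| Observed difference < 4 mg | 27 vs 27 | 49.9% |
| Upper 95% confidence limit < 4 mg | 27 vs 27 | 2.55% |
| Upper 90% confidence limit < 4 mg | 27 vs 27 | 5.0% |
| Wilcoxon shifted by 4 mg, one-sided 0.025 | 27 vs 27 | 2.4% |

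With no true difference, at 27 vs 27 and one-sided 0.025, the shifted Wilcoxon test has 76.7% power and the t interval 79.3%.

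**The case against.** The strongest reply is that the essentials are prespecified: a null, a 20% margin, alpha, power and a 48-hour window. The analysis sentence is generic and does not exclude a margin-shifted Wilcoxon test, which is still a rank sum test. The simplest reading, a fixed 4 mg at one-sided 0.025, reproduces 27 exactly, so margin scale and sidedness are less open than they look. The error rates belong to rules the plan never states. The study is observational with a historical comparator, so exact control of alpha carries less weight than in a randomised trial, and a reader could compute an interval from the reported means, SDs and group sizes.

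Some of this stands. The 12% to 50% rates are conditional illustrations, not operating characteristics of the protocol. The unit of measurement and the meaning of 45 are side issues. The match at 27 is good evidence of what was intended, but it is an inference: a t-based calculation with a relative margin at one-sided 0.05 also arrives at 27 (79.7% power at 26, 81.1% at 27).

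The core is not answered. A test described as measuring differences, with no shift or interval mentioned, is on its ordinary reading a test of no difference. That a reader could repair the analysis later is not a prespecified primary analysis, and the protocol itself chose to state a null, a margin, alpha and power.

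**Conclusion.** The concern holds. As written, the plan does not test the hypothesis it was sized for, and any non-inferiority claim would need a rule that the documents do not contain. This should be corrected before the cohorts are compared.

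If non-significance were read as non-inferiority, the chance of passing a QLB that is truly 4 mg worse would be about 23% at 27 per group, against 2.5% under the one-sided level that reproduces the sample size. This rests on normal data with a common SD of 5.2 mg and a TEA mean of 20 mg. The mismatch between hypothesis and test does not depend on those assumptions. The sample size itself is correct on the simplest reading of its inputs.

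**What to change.** Add as the primary analysis:

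> QLB is declared non-inferior to TEA only if the upper limit of the confidence interval for the QLB versus TEA comparison of 48-hour cumulative opioid consumption lies below the 20% margin. A non-significant Wilcoxon test, or a point estimate below 20%, is not by itself evidence of non-inferiority.

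Before the cohorts are compared, the sponsor should also state:

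1. **Margin scale:** 20% of the observed TEA value (ratio limit 1.20), or a fixed amount such as 4 mg.
2. **Side of alpha**, and so the confidence level.
3. **Opioid-equivalent unit**, with the drugs and routes counted.
4. **Interval method:** either a difference or ratio of means with a bootstrap check for skew, or a Hodges-Lehmann or margin-shifted Wilcoxon interval, which keeps the planned rank method.

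The stated power must match these choices. Twenty-seven per group fits a fixed 4 mg at one-sided 0.025 (81% by the normal formula, 79% by t) or a relative margin at one-sided 0.05 (81% by t). It does not fit a relative margin at one-sided 0.025 (71% by t, 73% by the normal formula), which needs 33 per group by the normal formula or 34 by t. The sponsor should also say what 45 refers to. Unshifted Wilcoxon and Fisher tests can stay for secondary outcomes.

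**Cost.** A few sentences, though the four choices must be made first; no new data. Non-inferiority becomes harder to claim than under an informal reading. The rank option loses a little power if data are normal (about 77% against 79%). A fixed 4 mg stops being 20% if the TEA mean differs from 20 mg: 4/15 = 27% and 4/25 = 16%. A relative margin stays at 20%, but its power at 27 per group would be 47% at a TEA mean of 15 mg and 88% at 25 mg (SD 5.2 mg, one-sided 0.025). None of this addresses confounding from the historical control.

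### Repeated pain scores are compared only by unadjusted rank-sum tests, with no summary over time and no use of the pre-operative score listed for both non-randomised cohorts

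*Combined protocol and SAP*

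**What the plan says.** Data Analysis & Statistical Considerations contains the whole analysis plan: descriptive statistics and "group comparisons via Wilcoxon rank sum or fisher exact tests to measure differences between cohorts in opioid consumption, pain scores with rest and activity", plus the other secondary measures. It gives no covariate, repeated-measures method, summary measure, key pain time or multiplicity rule.

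The NRS-11 paragraphs for both cohorts give the score the same standing: "The 11-point Numeric Rating Scale (0-10) will be used as a secondary outcome measure".

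- **Prospective cohort (Assessments, NRS-11).** "Two measures will be taken with each assessment, one at rest and one with coughing". On timing: "These will be conducted preoperatively, 30 minutes after arrival to PACU, and at time points 8 hrs., 24 hrs., 36 hrs. 48 hrs, 72 hrs," and then daily to 168 h.
- **Historical cohort (NRS-11 paragraph of the historical-data section).** "These will be collected from the preoperative assessment record, 30 minutes after arrival to PACU, and at time points 8 hrs., 24 hrs., 36 hrs.", followed by 48 and 72 h. Rest and coughing are not separated here, and chart items are to be used where available.

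Sample Size Justification states an error rate, "given an alpha of 0.05 and a power of 0.8", but only for 48-hour opioid consumption.

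**The concern.** A rank-sum test takes one value per patient. Each patient can contribute six shared post-operative scores, or twelve if rest and activity are separate, and the plan does not say how they become one value. The natural reading is a separate test at each time. That yields a set of unranked p-values with no overall answer, and a patient with a missing chart entry drops out of that time's test.

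The unused pre-operative score matters more here than in a randomised trial. One cohort is prospective, the other historical, and Selection of Subjects gives them different criteria. If they differ in pain before surgery, part of that difference carries into the post-operative comparison. The plan lists the one measurement that could address this directly and does nothing with it beyond description.

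At stake is how clearly the study can speak about analgesia. Purpose of the Study expects pain relief to be about the same in the two groups, and a result on opioid use is hard to interpret without a clear statement on pain.

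**Working it through.** **1. The plan's own figure.** The only error rate and power in the documents belong to the primary outcome. The margin is 20% of 20 mg = 4 mg and the SD is 5.2 mg. With two-sided 0.05 (one-sided 0.025), n per group = 2 × (1.96 + 0.8416)² × 5.2² / 4² = 26.5, rounded up to 27, or 54 in total, as stated. One-sided 0.05 would give 21 per group. So 0.05 is read as two-sided. Its use for each pain test is my assumption.

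**2. Number of tests.** There are six shared post-operative times. One score per time gives 6 tests; rest and activity at each time give 12.

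**3. Chance of at least one false difference at 0.05 per test.** If the tests were independent:

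- 6 tests: 1 − 0.95⁶ = 26.5%
- 12 tests: 1 − 0.95¹² = 46.0%

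Scores within a patient are correlated, so the real figure is lower. It was simulated with 27 per group, rounded 0-10 scores, assumed mean 4 and SD 2.5, and 4,000 runs per setting. Two correlation patterns over time were used, constant and decaying. Each range covers both patterns and, for 12 tests, rest-activity correlations of 0.5 and 0.7.

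| Between-time correlation | 6 tests | 12 tests |
|---|---|---|
| 0.3 | 24-25% | 36-40% |
| 0.5 | 21-22% | 34-39% |
| 0.7 | 18-19% | 28-35% |
| 0.8 | 15-17% | 24-30% |

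With the independent case as the upper end, the ranges are about 15-26% for six tests and 24-46% for twelve. A second simulation with 45 against 30 patients, SD 2.2 and rest-activity correlation 0.6 gave 17-24% and 28-40% over between-time correlations 0.7 to 0.3.

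**4. Gain from combining times.** Assumed: 45 against 30 patients, SD 2.2, a 1.2-point difference at every time, between-time correlation ρ. The variance of a mean of T scores relative to one score is (1 + (T − 1)ρ)/T.

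- Five times (30 min to 48 h): 0.44, 0.60 and 0.76 at ρ = 0.3, 0.5 and 0.7
- Six times (30 min to 72 h): 0.42, 0.58 and 0.75

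Normal approximation: the standard error at one time is 2.2 × √(1/45 + 1/30) = 0.519, so 1.2/0.519 = 2.31 and power is Φ(2.31 − 1.96) = 64%. For the five-time mean, dividing 2.31 by √0.44, √0.60 and √0.76 gives 3.49, 2.99 and 2.65, and power of 94%, 85% and 76%. Simulated rank-sum tests on rounded 0-10 scores run a little lower: 57-60% for 48 h alone and 70-91% for the five-time mean. The six-time variance factors are almost the same, so including 72 h loses nothing if the difference persists to then.

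**5. Gain from baseline adjustment alone.** With correlation r between pre- and post-operative pain, residual variance is multiplied by 1 − r². Starting from 80% power at one time:

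| r | 1 − r² | Power |
|---|---|---|
| 0.1 | 0.99 | 80.4% |
| 0.2 | 0.96 | 81.6% |
| 0.3 | 0.91 | 83.6% |
| 0.4 | 0.84 | 86.4% |
| 0.5 | 0.75 | 89.9% |

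The documents do not give r.

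**6. Baseline imbalance.** If the cohorts differ by d points before surgery, an unadjusted mean comparison carries a bias of slope × d. With equal pre- and post-operative SDs the slope equals r, so r = 0.3 passes on 0.3 of each point of imbalance and r = 0.5 passes on 0.5.

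**The case against.** **Separate testing is not stated.** A rank-sum test on a per-patient average would also fit the wording. This stands: the error rates in the working are conditional on the natural reading. The gap remains, because no average or key time is defined.

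**A reader might infer a false-difference risk of about one in three.** That needs twelve moderately correlated tests at 0.05. The analysis section does mention rest and activity, but the historical paragraph promises no such split. With one chart score per time the figure cannot exceed 26.5%.

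**A reader might infer that ignoring the pre-operative score wastes much power.** The 70-91% comes from averaging five times, with no baseline term in the calculation. The stronger reason to use the pre-operative score is imbalance. Even that correction is partial, since one cohort's score is a study assessment and the other's comes from the chart.

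**An average can hide a real difference.** Background & Significance says the epidural usually runs for two days and expects prolonged relief from the liposomal drug, so the difference may vary over time. With a 1.2-point shift at 36 and 48 h only, simulation gives the 30 min to 48 h average 17-27% power, against 59-60% for the 48 h test. This stands. It is the reason to cover all shared times and keep time-specific estimates.

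**A false difference would mostly count against the expected similarity.** True, and pain is secondary. But scattered p-values are no evidence of similarity either; an overall estimate with an interval speaks to that question directly.

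**Conclusion.** The concern holds for this secondary outcome. The plan compares repeated pain scores without a summary over time and leaves the pre-operative score unused, in cohorts where baseline imbalance is a real possibility. A better method is available from measurements the plan already lists.

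The size depends on assumptions that the documents do not settle: 0.05 per pain test, the number of tests, the SD, the correlations, and 45 against 30 patients (the plan does not say whether 45 is the prospective cohort or the total). The false-difference risk is at least about three times the nominal 5% on the six-test reading. The power gain from combining times is material only if the difference is similar across times. The gain from baseline adjustment is small unless r reaches about 0.4.

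A reader might extend this to the primary analysis. The documents do not support that: 48-hour opioid consumption is one value per patient, and its error rate is not affected by how pain is tested.

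**What to change.** Pre-specify one main pain comparison. Analyse rest and activity separately only where the historical records hold both scores; otherwise use one score per time.

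- **Model:** a mixed model over all shared times, 30 min to 72 h, with cohort, time, cohort × time and pre-operative NRS. ANCOVA on the per-patient mean is a simpler alternative.
- **Main result:** the time-averaged cohort difference with a 95% CI.
- **Supporting results:** time-specific differences with CIs, labelled descriptive.
- **Data:** tabulate missing scores by cohort and time. The mixed model keeps patients who lack some times, on the assumption that the gaps are explained by observed data.

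One such test has a 5% false-positive rate. Two (rest and activity) have 1 − 0.95² = 9.75% if independent, and less if positively correlated.

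The cost is a few lines of text and one more model. The single-score version needs only measurements already listed; the version by condition depends on what the charts contain. The downside is dilution of a difference confined to a few times, which the time-specific estimates are kept to show.

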Quantitative observational comparative effectiveness of quadratus lumborum block with liposomal bupivacaine (Exparel®) versus thoracic epidural analgesia in patients undergoing laparoscopic colectomy

NCT03827291

Document Date: 09/27/2022

Purpose of the Study

We believe that a quadratus lumborum block with liposomal bupivacaine(Exparel®) or a quadratus lumborum block with an admixture of bupivacaine will provide roughly equivalent analgesia and opioid use when compared with postoperative analgesia in a historical cohort that received thoracic epidural analgesia. We believe participants who receive the quadratus lumborum block will result in improved early mobilization, fewer complications such as block failure, urinary retention, and pruritis, and decreased overall pharmacy costs compared to the patients who received thoracic epidural analgesia.

Background & Significance

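### Fisher's exact test is conservative for the complication comparisons; Boschloo's exact test is never less powerful, but its gain runs from none to about 14 points depending on the final group sizes

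*Combined protocol and SAP*

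**What the plan says.** Data Analysis & Statistical Considerations plans descriptive statistics and "group comparisons via Wilcoxon rank sum or fisher exact tests to measure differences between cohorts". The Wilcoxon test suits opioid use and pain scores, so the binary outcomes fall to Fisher's exact test. The section gives no sidedness, no significance level for secondary outcomes, no event rates, no effect estimate or interval, and no multiplicity rule.

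The binary outcomes carry part of the study's rationale. Purpose of the Study expects "fewer complications such as block failure, urinary retention, and pruritis" with the quadratus lumborum block (QLB). The Assessments text lists the opioid-related events for both cohorts: "Incidence of nausea, vomiting, ileus, constipation, orthostasis, pruritis, urinary retention, respiratory depression". Block or epidural success and technique-related events come on top of these eight.

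Three figures bear on size. Sample Size Justification says "a total of 54 subjects (27 in each group) would be required" and then "We plan on recruiting 45 subjects to account for dropout", without saying whether 45 is the prospective cohort or the total. The Assessments text adds "Historical data of 30 patients that meet inclusion criteria and meet no exclusion criteria" for the epidural (TEA) cohort. The only error rate and power stated, "given an alpha of 0.05 and a power of 0.8", belong to the primary opioid comparison.

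**The concern.** Fisher's test conditions on both margins of the 2x2 table. Here only the two cohort sizes are fixed; the total number of events is random. Because the conditional distribution is coarse with about 30 patients per group, the test rejects less often than 5% under the null and loses power.

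Boschloo's test takes Fisher's p-value as its statistic and calibrates the cut-off over the unknown common event rate. Its rejection region therefore contains Fisher's, and its size stays at or below 5%.

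At stake is the chance of detecting a real difference in complications, which is modest with so few patients. No power is promised for these outcomes, so nothing stated in the plan is contradicted.

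**Working it through.** **The plan's own figure first.** Sample Size Justification states "A difference in opioid consumption less than 20% would be considered non-inferior", with 20 mg and SD 5.2 mg, so the margin is 0.20 × 20 = 4 mg. With a true difference of zero:

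n per group = 2 × (1.960 + 0.842)² × 5.2² / 4² = 26.5, rounded up to 27, or 54 in total.

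The stated 54 reproduces with one-sided 0.025, so the 0.05 acts as a two-sided level. (One-sided 0.05 would give 21 per group.) This figure is unaffected by what follows.

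**Inputs for the binary check.**
- Test: Fisher, from the analysis section. Two-sided 5% is an assumption.
- Sizes: 27 per group, 30 historical and 45 recruited, from the documents. The values between 30 and 45 are illustrative, for example 45 less dropout.
- Event rates: assumed, because the documents give none. QLB v TEA: 5% v 20%, 5% v 25%, 10% v 30%.

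**Method.** Enumerate every table with a events among n₁ and b among n₂. For a rejection region R:

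Power(p₁, p₂) = Σ over (a, b) in R of Bin(a; n₁, p₁) × Bin(b; n₂, p₂).

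Maximum size = the largest value of Power(p, p) over the common rate p.

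Fisher's region is two-sided Fisher p ≤ 0.05. Boschloo's region is Fisher p ≤ c, with c the largest cut-off that keeps maximum size ≤ 0.05. For example, c is 0.063 at 27 v 30 and 0.060 at 45 v 30.

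**Results.** Power cells are in %, Fisher → Boschloo, with the gain in points.

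| QLB v TEA | Max size, Fisher | Max size, Boschloo | 5% v 20% | 5% v 25% | 10% v 30% |
|---|---|---|---|---|---|
| 27 v 27 | 2.6% | 4.5% | 19.0 → 30.7 (+11.7) | 36.1 → 50.0 (+13.9) | 31.2 → 42.8 (+11.6) |
| 27 v 30 | 3.6% | 5.0% | 26.3 → 36.5 (+10.2) | 46.5 → 56.0 (+9.5) | 41.3 → 47.4 (+6.1) |
| 30 v 30 | 2.7% | 4.7% | 24.1 → 33.5 (+9.4) | 43.6 → 52.7 (+9.1) | 37.2 → 42.5 (+5.3) |
| 33 v 30 | 4.3% | ≤ 5% | +1.0 | +1.9 | +4.0 |
| 35 v 30 | 4.6% | ≤ 5% | +1.0 | +2.1 | +4.2 |
| 40 v 30 | 3.9% | 4.7% | 42.9 → 42.9 (0) | 63.6 → 63.6 (0) | 52.6 → 52.6 (0) |
| 42 v 30 | 4.0% | ≤ 5% | 0 | 0 | 0 |
| 45 v 30 | 3.7% | 4.9% | 43.8 → 50.7 (+6.9) | 63.6 → 69.7 (+6.1) | 52.4 → 57.1 (+4.7) |

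The gain is therefore not a smooth function of sample size. It can be large at one size and vanish a few patients away.

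**One table as illustration.** With 2/27 v 8/27 events, Fisher gives p = 0.076 and Boschloo p = 0.040.

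**What using the full 5% does across outcomes.** Take the eight listed opioid-related events as independent tests (an assumption), each at the 27 v 27 maximum size. The chance of at least one false positive is:
- Fisher: 1 − (1 − 0.0263)⁸ = 19%
- Boschloo: 1 − (1 − 0.0446)⁸ = 31%

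**The case against.** The strongest reply is that Fisher's test is valid and standard, that conditioning on the margins is a long-standing choice between legitimate methods, and that these outcomes are secondary. All of that is true, and it is why this is not an error in the plan. It does not make the choice neutral: Boschloo keeps the same nominal level, loses none of Fisher's rejections, and gains materially at several of the plan's own sizes.

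A second reply concerns dropout. If 45 is the prospective cohort, the analysed number will be lower. Dropout of 7% to 13% leaves 42 to 39 patients, where the gain in these scenarios is at most about 1 point. This stands, and it limits the benefit.

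A third reply is that sharpening a crude test does little for a non-randomised comparison with a historical cohort. Block failure is also measured differently: by pinprick prospectively, and from anesthesia and pain service notes retrospectively. This stands too. A more powerful test can make a biased difference significant more easily.

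Three stronger readings are tempting, and the documents' sizes do not support them:
- That Fisher's true error is at most 3.6% anywhere from 27 to 45 v 30. It reaches 4.3% at 33 v 30 and 4.6% at 35 v 30.
- That the gain is 5 to 10 points throughout. It runs from zero to about 14.
- That the switch costs nothing. It needs no more patients and keeps each test at or below 5%, but with no multiplicity rule the chance of some false positive rises.

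**Conclusion.** The point holds as an efficiency improvement of variable size. Fisher's test is conservative at the sizes the documents name, and Boschloo's test is never less powerful at the same 5% level. The gain is worthwhile at 27 v 27, 27 v 30, 30 v 30 and 45 v 30, small at 33 or 35 v 30, and essentially nil at 40 or 42 v 30.

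This rests on two-sided 5% testing and on assumed event rates. The final group sizes are also uncertain, because the role of the 45 is not stated. In every scenario tabulated with power, both tests stay below 80%, so the change does not make the complication comparisons well powered. It affects neither the primary outcome nor the 54-patient calculation, and it does not deal with confounding.

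**What to change.** In Data Analysis & Statistical Considerations:

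1. Replace Fisher's exact test with two-sided Boschloo's exact unconditional test for the crude binary comparisons. Fix it before the data are seen, with the two-sided Fisher p-value as the test statistic, since the comparison above was checked for that version.
2. Report each binary comparison as a risk difference with a 95% score interval. This is useful at any final size, including those where the new test gains nothing, because the plan now offers only frequencies and tests.
3. State that the binary secondary results are unadjusted for multiplicity and exploratory, and that they do not correct for differences between the prospective and historical cohorts.

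The cost is one changed phrase and two added sentences; the test is in standard software and no extra patients are needed. The price in error control is the higher chance of at least one false positive shown above, which the third item discloses but does not remove.
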